4.2.6. Other Efficacy Variable(s)

4.2.6.1. Definition

Formulae to be used for derived variables, including data conversions, are provided in [Table 5](#). In the derivation of durations described below, no imputation of the start and/or end date/time will be performed.

Table 5. Calculations and Conversion Formulae

Measurement	Formula
Time to onset of complications after initiation of treatment	
Defined as the relative time in days from the first dose of study drug until the first occurrence of any of the following complications:
 
 - Bacterial superinfection, - Exacerbation of underlying pulmonary disease, - Cardiovascular and cerebrovascular event, - Respiratory Failure - Clodistridium difficile associated diarrhea. - Other RSV complications 
If a subject has a complication before the first intake, time will be set to 0.
 
Time to onset of complications will be censored at date of study completion/discontinuation for subjects without complications

Hospital readmission for respiratory reasons	
Medical review will be done immediately before data base lock on a list with unique coded adverse events (MedDRA Preferred Terms) for subjects who are re-admitted to the hospital to indicate which subjects were re-admitted for respiratory reasons

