4.1. Inclusion Criteria

Each potential subject must satisfy all of the following criteria to be enrolled in the study:

1. Criterion modified per Amendment 2:
 - 1.1. Criterion modified per Amendment 3:
 - 1.2. Men or women ≥ 18 years of age (or the legal age of consent in the jurisdiction in which the study is taking place), defined at the time of randomization.
2. Hospitalized (or in emergency room prior to hospitalization) at the time of randomization and unlikely to be discharged for the first 24 hours after randomization.
3. Criterion modified per Amendment 2:
 - 3.1. Diagnosed with RSV infection based on PCR-based assay with or without co-infection with another respiratory pathogen (eg, influenza, human metapneumovirus, or bacteria).

NOTE: in cases where commercial PCR-based assays are not available at the site, the sponsor should be consulted for agreement on the assay to be used.

4. Criterion modified per Amendment 2:
 - 4.1. Has an acute respiratory illness with signs and symptoms consistent with a viral infection (eg, fever, cough, nasal congestion, runny nose, sore throat, myalgia, lethargy, shortness of breath, or wheezing) with onset ≤ 5 days from the anticipated time of randomization.

NOTE: The viral infection may present in any way as long as the underlying precipitant of the illness is considered by the investigator to be due to RSV infection. Examples of such an illness include:

- An upper or lower viral respiratory tract infection (eg, “flu-like illness”)
- Pneumonia
- Respiratory distress
- Asthma exacerbation
- Chronic obstructive pulmonary disease (COPD) exacerbation

5. Criterion modified per Amendment 2:
 - 5.1. With the exception of the RSV disease, medically stable on the basis of medical history, physical examination, vital signs, and 12-lead ECG performed at screening. If there are abnormalities, they must be consistent with the underlying illness in the study population and/or the RSV infection. This determination must be recorded in the subject’s source documents and initialed by the investigator.

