1.1. Trial Objectives

Primary Objective

The primary objective is to determine in adults who are hospitalized with RSV infection the dose-response relationship of multiple regimens of ALS-008176 on antiviral activity based on nasal RSV shedding using quantitative real-time reverse transcriptase-polymerase chain reaction (qRT-PCR) assay.

Secondary Objectives

The secondary objectives are to determine in adults who are hospitalized with RSV infection:

- The impact of ALS-008176 on the clinical course of RSV infection including:
 - Duration of hospital stay.
 - Duration of supplemental oxygen.
 - Evolution of Activities of Daily Living (ADL) as assessed by Katz ADL score.
 - Time to clinical stability.
 - Improvement on the ordinal scale.
 - Rate of mortality and complications.
- The time to cessation of nasal RSV shedding.
- The impact of ALS-008176 on the emergence of resistant strains of RSV.
- The safety and tolerability of ALS-008176.
- The pharmacokinetics (PK) of ALS-008112 and ALS-008144 (and other metabolites, if applicable) in plasma.

- The relationship between the PK and pharmacodynamics (PD; antiviral activity, clinical symptoms, and selected safety parameters) after single (loading dose [LD]) and repeated oral dosing (maintenance dose [MD]) of ALS-008176.

Exploratory Objectives

The exploratory objectives are to evaluate in adults who are hospitalized with RSV infection:

- The relationship between viral kinetics and clinical outcome, including the relationship between RSV RNA viral load and:
 - Oxygen supplementation.
 - Duration of hospitalization.
 - Katz ADL.
 - Clinical stability.
- The impact of the baseline viral subtype and genotype on the antiviral response.
- Onset of complications after initiation of treatment.
- The impact of ALS-008176 on the clinical course of RSV during and following hospitalization as assessed by the subject in the electronic Clinical Outcome Assessment (eCOA) using various scoring systems.
- The impact of RSV and its treatment on health-related quality of life (HRQoL) as assessed by the subject in the eCOA.
- The relationship between the Katz ADL and the subject eCOA responses.
- Medical resource utilization to manage subjects.
- The comparison of the RSV RNA viral loads measured in mid-turbinate nasal swabs and endotracheal samples from intubated subjects.
- To explore the evolution of diffusing capacity of the lung for carbon monoxide (DLCO) and spirometry in subjects hospitalized due to RSV infection.

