 - Supplemental oxygen above pre-RSV disease level (regardless of method used) from study treatment initiation to Day 7.
 - Oxygen delivered by noninvasive ventilator support (eg, continuous positive airway pressure) and/or invasive ventilator support (eg, endotracheal-mechanical ventilation or mechanical ventilation via tracheostomy).
 - Subjects (proportion) who started antibiotic use after the first dose of the study drug.
- Disease status and presence of complications with onset after treatment initiation:
 - Bacterial superinfections reported as AEs (eg, pneumonia, acute otitis media, sinusitis, bronchitis, bacteremia).
 - Exacerbations of underlying pulmonary disease (eg, asthma, chronic obstructive pulmonary disease).
 - Cardiovascular and cerebrovascular events (eg, myocardial infarction, congestive heart failure exacerbation, arrhythmia, stroke).
 - Respiratory failure
 - *Clostridium difficile* associated diarrhea
 - Other

- Duration and severity of signs and symptoms of RSV infection as assessed by the respiratory infection patient-reported outcome (RI-PRO) questionnaire and additional questions about health and functioning completed by the subject in the eCOA.
- HRQoL assessed by the EuroQoL 5 Dimension visual analogue scale (EQ-5D VAS) completed by the subject in the eCOA.
- Hospital readmission for respiratory reasons up to the Day 28 follow-up visit.
- RSV RNA viral load (AUC) as measured by qRT-PCR of endotracheal samples in intubated subjects.
- Lung function measured by the DLCO and spirometry test.
- RSV infectious viral load as measured using a quantitative viral culture (plaque assay).

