4.2.4.2. Analysis Methods

To compare incidences across treatment groups (for the need for ICU stay, oxygen support, supplemental feeding or supplemental hydration, for the all-cause mortality, for the subjects with undetectable viral load per time point and for the presence of complications), logistic regressions will be used, with treatment as fixed effects and strata as part of the stratifying variables (ie. stratified logistic model). Other covariates and or baseline indicators may be included in the model when of predictive value, such as baseline \log_{10} viral load, smoker (yes/no), the presence/absence of co-morbid diseases, presence/absence of co-morbid diseases associated with risk for lower respiratory tract disease, presence/absence of other conditions/therapy of potential interest, days since symptom initiation, RSV subtype, use of corticosteroids, supplemental oxygen at baseline and age as continuous variable. Stepwise selection will be used to identify the prognostic factors for each of the different models for the different incidence parameters. A significance value of 0.05 is required for a variable to enter the model and a significance value of 0.10 is required to stay in the model. The odds ratios including 95% confidence interval of active groups versus placebo will be derived from the final model using appropriate contrasts. Exact logistic regression models will be used in case the incidence of the events is low (< 10 events).

Time-to-events variables will be analyzed in an exploratory sense using Kaplan-Meier analysis, A summary table including number of subjects included in the analysis, number of subjects censored, 25th and 75th percentiles and median time to event, with 95% confidence intervals based on log-log transformation method, will be presented. The data will be presented graphically using the Kaplan-Meier estimate of the survival function.

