2) Adverse event: start date: JAN2017- stop date 27JAN2017 As the AE stops before or at the start of the treatment phase, it is only assigned to the Screening phase.

Remarks:

In addition to the date information, time information is taken into account to allocate AEs to phases.

Step 2: Combination of Events

Overlapping/consecutive events are defined as events of the same subject with the same preferred term who have at least 1 day overlap or for which the start date of an event is 1 day after the end date of the preceding event. Overlapping/consecutive events may be combined into one AE or not, according to the following rules:

- 1) In case a non-active phase (e.g. Screening) is followed by an active phase, and the overlapping/consecutive events start in both phases, they are allocated to their respective phase and are considered as separate events.
- 2) In case overlapping/consecutive events start within a single phase, they are considered as one and the same AE. The individual events who contribute to this AE are retained as individual records in the ADAM database but are assigned the same onset, phase, and total duration.
- 3) In case an active phase is followed by a non-active phase (e.g. Follow-Up), and the overlapping/consecutive events start in both phases, they are allocated to the active phase only and are considered as one and the same AE. The individual events who contribute to this AE are retained as individual records in the ADAM database but are assigned the same onset, treatment phase, and total duration.

Remarks:

- 1) Events can only be combined into one and the same AE if their start and stop dates are complete.
- 2) In case the completely missing end date is imputed, this date is also considered as a complete date.

- 3) Time is not considered when determining overlap of events.
- 4) Adverse events will be reported from the informed consent date on (i.e. in the screening period) until trial termination.

Analysis Methods

A Summary will be provided for the following treatment-emergent adverse events per phase (Treatment phase, Follow-up phase) and for the combination of Treatment and Follow-up phase: any adverse events, serious adverse events, deaths due to AE, adverse events by toxicity grade, AEs at least possibly related to study medication, AEs for which study medication was permanently stopped, serious adverse events that were at least possibly related to study medication. There will be no formal statistical testing.

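### Complications that began before the first dose count as day-0 events in the SAP's exploratory time-to-complications variable, which is meant to capture onset after treatment starts

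*SAP*

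**What the plan says.** SAP section 4.2.6.1 (Table 5) defines the variable as follows: "Defined as the relative time in days from the first dose of study drug until the first occurrence of any of the following complications". The list covers bacterial superinfection, exacerbation of underlying pulmonary disease, cardiovascular or cerebrovascular event, respiratory failure, C. difficile diarrhea and other RSV complications. Two handling rules follow:

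- For a complication that precedes dosing, the rule is: "If a subject has a complication before the first intake, time will be set to 0".
- For censoring, a separate sentence in the same table cell applies: "Time to onset of complications will be censored at date of study completion/discontinuation for subjects without complications".

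The exploratory objective in SAP section 1.1 is "Onset of complications after initiation of treatment". The exploratory endpoint in SAP section 4.2 is "Disease status and presence of complications with onset after treatment initiation", and Protocol section 2.1.2 carries the same restriction.

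SAP section 4.2.6.2 names no analysis for the time variable. The general rule in section 4.2.4.2 is: "Time-to-events variables will be analyzed in an exploratory sense using Kaplan-Meier analysis". The accelerated failure time comparison in that section applies only to variables for which it is specified, and it is not specified here. What 4.2.6.2 does compare between arms is the presence of complications, by stratified (exact) logistic regression.

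**The concern.** A variable meant to show when complications arise on treatment should not count complications that preceded treatment. Doing so has two consequences.

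1. Events that the drug cannot influence enter every arm, so the curves are pulled together.
2. Because only the first occurrence counts, a subject placed at time 0 cannot contribute a new complication that arises on treatment.

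Pre-dose cases are conceivable. Protocol section 4.1, criterion 4, lists examples of qualifying illness, among them "Chronic obstructive pulmonary disease (COPD) exacerbation", asthma exacerbation and pneumonia. Exacerbation of pulmonary disease is a listed complication, and pneumonia is given as an example of bacterial superinfection. Adverse events are also captured before dosing: "Adverse events will be reported from the informed consent date on (i.e. in the screening period) until trial termination".

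**Working it through.** **Are these subjects events?** Table 5 does not use that word. It gives them a time of 0, keeps them in the variable, and reserves censoring for subjects without complications. A subject with a pre-dose complication is not in that group, so the record is an uncensored time of 0. No other section excludes these subjects or provides an analysis without them.

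**Where a zero makes sense.** Table 1 in SAP section 4.2.4.1 sets time to 0 for recovery variables, such as end of oxygen or feeding support, when no support was needed. There, 0 is the best possible result. In a complication variable, 0 is the worst.

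**Size.** The documents give no complication rate, so there is no planned figure to reproduce. The inputs below are assumptions: post-dose risk p by day 28 of 20% on placebo and 10% on an active arm, and pre-dose prevalence q equal in both arms. Under the rule:

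- Kaplan-Meier estimate just after day 0: S(0) = 1 − q
- Cumulative incidence at day 28: q + (1 − q)p
- Difference between arms: (1 − q)(0.20 − 0.10)

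| q | S(0) | Placebo v active at day 28 | Difference | Risk ratio | Odds ratio |
|---|---|---|---|---|---|
| 0% | 1.00 | 20% v 10% | 10 points | 0.50 | 0.44 |
| 10% | 0.90 | 28% v 19% | 9 points | 0.68 | 0.60 |
| 30% | 0.70 | 44% v 37% | 7 points | 0.84 | 0.75 |
| 50% | 0.50 | 60% v 55% | 5 points | 0.92 | 0.81 |

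Example at q = 30%: placebo 0.30 + 0.70 × 0.20 = 0.44; active 0.30 + 0.70 × 0.10 = 0.37; ratio 0.37/0.44 = 0.84.

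**Effect on the planned summary.** SAP section 4.2.4.2 reports quartiles of time to event. Once q exceeds 25%, the 25th percentile is 0 in each arm whatever the drug does.

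**Hidden on-treatment complications.** If subjects with a pre-dose complication have the same post-dose risk as the others, the share with an uncounted on-treatment complication is q × p. At q = 30% this is 0.30 × 0.20 = 6% on placebo and 0.30 × 0.10 = 3% on active, or 1.8 and 0.9 of 30 subjects per arm.

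**Direction on a hazard scale.** No Cox model is planned for this variable, so this is illustration only. Large simulated samples used a true post-dose hazard ratio of 0.5 and 30% placebo incidence over 28 days. With the time-0 subjects counted, the fitted ratio was 0.64, 0.71 and 0.79 at q = 10, 20 and 30%. Across placebo incidences of 20 to 40% it was 0.61 to 0.67 at q = 10% and 0.74 to 0.84 at q = 30%. With those subjects removed it stayed at 0.49 to 0.51. Every case moved toward no effect.

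**The case against.** The strongest reply is that little depends on this variable. It is exploratory in both documents and would receive only a default Kaplan-Meier summary, with no between-arm test or estimate specified. This stands.

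A reader might infer from the risk and odds ratios above that the planned logistic comparison is diluted. The documents do not establish that. The section 4.2.6.2 heading already limits that analysis to onset after treatment initiation, and nothing says the Table 5 rule carries over. The text beneath the heading tabulates any occurrence of complications, so the point is open. The ratios apply to that model only if pre-dose cases are also counted there.

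A reader might also infer that a secondary objective is compromised, because mortality and complication rates are listed among the secondary objectives. A rate is answered by the incidence tabulation and the logistic model. The time variable corresponds to a separate, exploratory objective.

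Finally, a reader might infer that many subjects are affected. Criterion 4 describes how the index illness may present; it does not say that the presentation is recorded as a complication. Bacterial superinfections are those reported as adverse events, collection begins at consent, and dosing starts within 4 hours of randomization. The pre-dose window could therefore be short and q small. The case report form that would settle this is not reproduced. Respiratory distress, another qualifying presentation, is not the listed complication, which is respiratory failure.

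None of this defends the rule itself. It limits the rule's reach and leaves its size unknown.

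**Conclusion.** The derivation is wrong as written. It counts pre-dose complications as events in a variable defined by onset after treatment starts, lowers the Kaplan-Meier curve at day 0 by the pre-dose prevalence, and drops later on-treatment complications in the same subjects. The conflict of wording is certain, given the inference from the censoring sentence. The direction, toward no difference, follows because treatment cannot affect pre-dose events and randomization balances them in expectation. The size is not known: the difference in cumulative incidence shrinks by the factor 1 − q, and q is not in the documents.

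The consequence is modest. The rule does not inflate type I error, so it gives no ground for expecting a false claim of benefit, and it does not touch the primary endpoint. It is an inconsistency in an exploratory variable that should be corrected because the correction is simple and the resulting curve would otherwise mislead.

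**What to change.** In SAP Table 5, delete the time-0 rule and define the event as the first listed complication with onset at or after the first dose. Keep subjects with a pre-dose complication in the risk set for a new post-dose onset, and censor them as others are if none occurs. Report pre-dose complications by arm with the baseline characteristics. In section 4.2.6.2, state the same post-dose restriction for the frequency table and the logistic model, so that the text agrees with its heading.

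The cost is SAP wording and a small programming change before database lock. The definition already depends on onset timing relative to first dose, so no new data appear to be needed. For a new episode that overlaps a pre-dose one, SAP section 4.3.1 already treats adverse events starting in screening and in the treatment phase as separate, and that convention could be reused. Counting worsening of a pre-dose complication would need its own definition and is not required for this correction.

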4.2.6.2. Analysis Methods

The amount of supplemental oxygen

The amount of supplemental oxygen will be listed over time.

Subjects (proportion) who started antibiotic use after the first dose of the study drug

Frequency tabulations will be given for the need for antibiotics related to RSV infection complications, as recorded in the CRF.

Disease status and presence of complications with onset after treatment initiation

Frequency tabulations will be given for any occurrence of RSV complications (Bacterial superinfections, Exacerbations of underlying pulmonary disease, Cardiovascular and cerebrovascular events, Clostridium difficile associated diarrhea, Respiratory failure, Other).

To compare incidence in the presence of complications across treatment groups a stratified (exact) logistic regression model as specified above will be used.

Detailed information on the type of complications, seriousness, severity and outcome will be given as part of the safety analysis (see section 4.3.1).

Hospital readmission for respiratory reasons

Frequency tabulations will be given for Hospitalization readmissions for respiratory reasons.

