8. PRESTUDY AND CONCOMITANT THERAPY

Prestudy therapies administered up to 7 days before first dose of study drug must be recorded at screening.

All subjects will receive supportive care according to local institution standard. While treatment guidelines and standards vary based on local practice and should be considered in the management of subjects, within the parameters of this study, it is recommended that supplemental oxygen can be administered or withdrawn, as appropriate to maintain an SpO₂ ≥93% (for subjects whose baseline SpO₂ is ≥93% when clinically stable).

Concomitant therapies must be recorded throughout the study beginning with start of the first dose of study drug to the Day 28 visit (±2 days). During hospitalization, concomitant medication will be recorded by the site staff in the eCRF. Upon discharge, subjects will be required to document use of concomitant medication in the electronic device in a medication log, which will serve as basis for recording the concomitant medication in the eCRF by the site staff.

Concomitant therapies should also be recorded beyond Day 28 in the subject's medical notes and reported by SAE forms (if applicable) only in conjunction with SAEs that meet the criteria outlined in Section 12.3.2.

All therapies (prescription or over-the-counter medications, including vaccines, vitamins, herbal supplements, home oxygen therapy; non-pharmacologic therapies such as electrical stimulation, acupuncture, special diets, exercise regimens) different from the study drug must be recorded in the eCRF. Recorded information will include a description of the type of the drug/therapy, treatment phase, the dose regimen, route of administration, and its indication. Modification of an effective preexisting chronic therapy should not be made for the explicit purpose of entering a subject into the study, however if a subject has received acute doses of a prohibited drug, switching to an alternative drug chosen at the discretion of the investigator is allowed.

Concomitant medications are permitted as indicated for the management of study subjects with the exception of the medications noted here. The following medications are not permitted during the study and for the time period prior to randomization as noted:

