4.1.8. Prior and Concomitant Medications

Medications taken 14 days before the Screening Visit and up to the Safety Follow-up Visit will be summarized by preferred term using the World Health Organization-Drug Dictionary for the ITT-i Set as frequency tables in 2 parts:

1. Prior medication: medication that started before the first dose of study drug, regardless of when dosing of the medication ended
2. Concomitant medication: medication received at or after the first dose of study drug, medication that was received before initial dosing and continued after initial dosing of study drug, or medication with missing stop date.

(Medication that started before the first dose of study drug and continued after the first dose of study drug will be summarized as prior medication and separately as concomitant medication.)

The part on concomitant medication will be shown by ATC class level up to level 3.

If a prior/concomitant therapy record misses components of its start and/or stop dates (time and/or day and/or month and/or year), the following actions will be taken:

1. In case of partial start or stop datetimes, the concomitant therapy records will be allocated to prior/concomitant using the available partial information, without imputations.
2. In case of a completely missing start date, the prior/concomitant therapy will be considered as having started before the trial.
3. In case of a completely missing end date, the prior/concomitant therapy will be considered as ongoing at the end of the trial.

Separate tables will be made for medication related to fever and not related to fever. Medication related to fever will be categorized as Acetaminophen/paracetamol, Ibuprofen, or other.

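### SAP 4.2.6.2 counts only antibiotics related to RSV complications, so it does not deliver the stated endpoint of any antibiotic started after first dose

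*SAP*

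**What the plan says.** Protocol 2.1.2 and SAP 4.2 list the same exploratory endpoint in the same words: "Subjects (proportion) who started antibiotic use after the first dose of the study drug". It has one condition, a start after the first dose, and no condition on why the antibiotic was given.

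SAP 4.2.6.2 repeats that endpoint name as a subsection heading. The whole analysis under it is: "Frequency tabulations will be given for the need for antibiotics related to RSV infection complications, as recorded in the CRF". Table 5 in SAP 4.2.6.1, which holds the derivations for the other efficacy variables, has no entry for antibiotic use.

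Three other places bear on the point:

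- SAP 4.1.8 summarises medication in the ITT-i set. Its concomitant category includes "medication that was received before initial dosing and continued after initial dosing of study drug", and the display rule is: "The part on concomitant medication will be shown by ATC class level up to level 3".
- Protocol Section 8 states: "Prestudy therapies administered up to 7 days before first dose of study drug must be recorded at screening". Later therapies are recorded from the first dose to the Day 28 visit, with their indication.
- SAP 4.2.6.1 allows for complications that precede dosing, in the time-to-onset derivation: "If a subject has a complication before the first intake, time will be set to 0".

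**The concern.** The heading names one quantity and the sentence beneath it specifies another. The endpoint asks how many subjects needed a new antibiotic once on study drug. The sentence asks how many needed an antibiotic for an RSV complication. If programmed as written, the table reports a subset of the new starts under the name of the full endpoint.

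The restriction also depends on a judgement about the reason for the antibiotic, which the SAP does not describe: it does not say who makes it, when, or by what criteria. Reasons are often mixed in this population. Eligible subjects may have RSV "with or without co-infection with another respiratory pathogen (eg, influenza, human metapneumovirus, or bacteria"), and pneumonia or a COPD exacerbation may be the presenting illness. An unrestricted count of new starts needs no such judgement.

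A second, weaker issue is timing. The endpoint turns on when the antibiotic started, and the analysis sentence does not mention it.

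**Working it through.** The documents give no antibiotic rate and no figure for this endpoint, so there is nothing to reproduce. The check sets the two definitions side by side.

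| Antibiotic started | Reason | Endpoint (Protocol 2.1.2, SAP 4.2) | Sentence in SAP 4.2.6.2 |
|---|---|---|---|
| After first dose | RSV complication | counted | counted |
| After first dose | any other or unstated | counted | not counted |
| Before first dose | RSV complication | not counted | not excluded by the sentence; the heading may exclude it |
| Before first dose | any other or unstated | not counted | not counted |

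The second row follows directly from the wording. The third depends on how the heading is read.

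In symbols, for one arm of N subjects in the ITT-i set:

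- a = subjects with a post-dose start for an RSV complication;
- b = subjects with a post-dose start, but none for an RSV complication;
- c = subjects with complication-related use begun before first dose and no post-dose start for a complication.

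The endpoint is (a + b)/N. If the heading limits the table to post-dose starts, the table gives a/N and falls short by b/N. If it does not, the table gives (a + c)/N, which differs from the endpoint by (c − b)/N and could err in either direction. None of a, b or c can be filled in from the documents.

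Could another output supply (a + b)/N? The only candidate is the summary in SAP 4.1.8. A drug begun before first dose and continued is shown there as prior and again as concomitant, so the concomitant rows mix continuing users with new starters. Subtracting the prior rows does not help, because prior medication also includes courses that ended before dosing. The stated proportion is therefore not produced anywhere.

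Elsewhere the SAP does write pre-dose status into the analysis text. In 4.2.4.2, need for ICU stay is limited to subjects not in the ICU before first dose. Supplemental oxygen is split by whether it was required before treatment, and feeding and hydration are handled similarly. The antibiotic endpoint has no equivalent rule.

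**The case against.** The strongest reply concerns timing. The sentence sits under a heading that already says the antibiotic started after first dose, and the SAP states in Section 1 that it is to be read with the protocol. The next subsection of 4.2.6.2 follows the same pattern: its heading limits complications to those with onset after treatment began, while its text mentions only any occurrence. The CRF page is not in the documents, and the item might carry a start date or be asked only after dosing. All of this stands, so pre-dose use entering the table is a possibility and not a finding.

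A reader might go further and infer that prior users are counted and pull the arms together. Suppose new starts among subjects not yet on antibiotics are 30% on placebo and 15% on active, and a fraction p of each arm is already on antibiotics, all flagged as complication-related and starting no new course. Over all subjects the endpoint ratio is 0.50 for any p. Counting prior users gives 0.20 + 0.80 × 0.30 = 44% against 0.20 + 0.80 × 0.15 = 32% at p = 20% (ratio 0.73), and 65% against 57.5% at p = 50% (ratio 0.88). The documents support none of these inputs. They also do not show that antibiotics given at admission for the qualifying illness would be recorded as needed for an RSV complication. The calculation shows a mechanism and is not an estimate.

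It can also be said that SAP 2.4 requires footnotes clarifying each display, that overall antibiotic use will be visible by ATC class, and that the endpoint is exploratory with only a frequency table. These limit the consequences. None of them removes the indication restriction or produces the missing proportion.

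**Conclusion.** The point holds for the indication restriction. As written, SAP 4.2.6.2 does not analyse the endpoint defined in Protocol 2.1.2 and SAP 4.2: antibiotics newly started after first dose for reasons other than an RSV complication are left out. This rests on the text alone and needs no assumption about rates or about the CRF.

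On timing the conclusion is narrower. The sentence states no start-after-first-dose rule, the heading may supply one, and pre-dose antibiotics are not explicitly excluded. The documents do not support saying that prior users will be counted.

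The size is unknown. Practical weight is modest: the endpoint is descriptive, outside the type I error control in SAP 4.2.1.1, and unconnected to the primary viral load analysis or the interim decisions. It still merits correction, because a protocol endpoint would otherwise go unreported while a table bears its name.

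**What to change.** In SAP 4.2.6.2, under the existing heading, specify for the ITT-i set, by arm, the number and proportion of subjects with at least one antibiotic whose start date/time is after the first dose, whatever the indication, derived from the prior and concomitant medication records. Keep the complication-related CRF item as a separate row, labelled as such. A display by antibiotic status at first dose is optional; the endpoint does not require it.

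State the rule for partial start dates on Day 1, because existing rules point different ways. SAP 2.1 sets a missing clock time to 00:00 for events, which would place every untimed Day 1 start before the first dose. SAP 4.1.8 allocates partial medication dates without imputation. Either can work, provided it is chosen before unblinding and the number of unresolved subjects is reported.

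The cost is one extra derivation and a change of SAP wording. The SAP 4.1.8 rules presuppose start and stop dates, so no new collection should be needed. However, Protocol Section 8 does not list start time among the recorded items, so some Day 1 starts may remain unresolved.
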